# 1 PROTOCOL SUMMARY

Title:	PREVAIL: PREVenting infection using Antimicrobial Impregnated Long lines
Full Title:	An unblinded, 2-arm randomised controlled trial to determine the effectiveness and cost effectiveness of antimicrobial impregnated (with rifampicin and miconazole) long lines (termed peripherally inserted central venous catheters, or AM- PICC (AM-PICC)) compared with standard PICC (S-PICC) for reducing blood stream infection (BSI).
Part I:	Randomised controlled trial
Phase:	III
Population:	
The trial population aims to include 858 babies who require the narrowest PICC (Premicath 1 French gauge (Fr)). Premicaths are designed for babies <1kg and most participants will be very preterm (born at <32 weeks of gestation).
 
A PICC is usually inserted after the first 2 days of age to administer fluids, medicines and nutrition.

Trial Sites and Distribution:	The trial will take place in 18 Neonatal Units (NNUs) in England.
Trial Duration Recruitment: Follow up:	
2 years.
 
Participant follow-up to ascertain the primary outcome (BSI):
 
 
• 48 hours after removal of the randomised PICC or;
 
• 48 hours after attempted insertion of randomised PICC
 
 
Participant follow-up to ascertain secondary outcomes:
 
 
• Until discharge from NNU or;
 
• Death or;
 
• 6 months (26 weeks) post randomisation (whichever is sooner).
 
 
Data will be based on routinely recorded clinical data collated by the Research Nurse (RN).
 
For long-term participant follow-up please refer to part II.

Description of Agent/ Intervention:	We will use a web-based interface to randomly allocate new born babies to S-PICC or AM-PICC). All PICCs used in the trial are CE marked medical devices used for their intended purpose. AM-PICCs can be distinguished from S-PICCs as rifampicin causes brown staining on the tubing. Hence, this is an unblinded trial.
Primary Outcomes:	Time to BSI based on any positive blood/CSF culture . (any positive bacterial or fungal blood/CSF culture will be included) taken between 24 hours after randomisation until 48 hours after PICC removal.

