- iv) The combination of rifampicin and an antifungal – miconazole - has not previously been evaluated in a RCT for its effect on BSI. Candidaemia is an infrequent, but well-recognised problem in very preterm neonates, and is associated with a high mortality rate (31). Use of miconazole may therefore be appropriate for this population.
- v) Emergence of resistant organisms is a major problem for NNUs. Rifampicin is known to cause emergence of resistant organisms, particularly when used as the sole antibiotic in therapeutic levels (32). However this may or may not occur with the very small dose in the AM-PICC. Rifampicin resistance may attenuate any reduction in BSI risk due to antibiotic impregnation over time. This has not been evaluated previously. Rifampicin resistance does not impact on NNU treatment regimens as this drug is not used routinely in NNUs.
- vi) Unlike more mature children, very preterm survivors of BSI are at increased risk of long-term neurological impairment, even when BSI is due to skin organisms (33). It is not known whether the reduction in BSI associated with antibiotic impregnated catheters is associated with a commensurate reduction in the risk of neurological impairment.

The trial is needed now because potential health gains are unlikely to be realised without robust evidence from a RCT. Clear evidence is needed of the effects of AM-PICC on BSI, the safety of AM-PICC, and on cost-effectiveness, before neonatologists will be willing or able to change purchasing decisions to adopt these devices in NNUs.

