### 4.2 Secondary Endpoint(s)

Outcomes captured up until 48 hours after PICC removal:

1. Rifampicin resistance in any isolate from blood/CSF culture.
2. Rifampicin resistance in any isolate from PICC tips.
3. Type of organism isolated from BSI.
4. Rate of BSI per 1000 PICC-days (including recurrent BSI).
5. Occurrence of 1 or more BSI.
6. Rate of catheter-related BSI per 1000 PICC days.
7. Rate of blood/CSF culture sampling per 1000 PICC days.
8. Duration of antimicrobial exposure from randomisation up to 48 hours after line removal.
9. Time to PICC removal.

Outcomes captured up until discharge home from neonatal care/death/6 months post randomisation:

10. Chronic lung disease 36 weeks postmenstrual age.
11. Necrotizing enterocolitis (NEC): Bell's stage II or III.
12. Treatment for retinopathy of prematurity.
13. Abnormalities on cranial ultrasound.
14. Time to full milk feeds after randomisation.
15. Total duration of parenteral nutrition from randomisation until discharge from NNU.
16. Death:
  - a) within 6 months (26 weeks) of randomisation
  - b) before discharge home from neonatal care
  - c) Time to death

For health economics outcomes, please refer to Part II: Economic Analysis.

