## **8.4 Procedures for Assessing Safety**

Adverse events whose causal relationship to the trial intervention (PICC) is assessed and judged by the investigator to be possibly, probably, or almost certainly related to the intervention that occur at the time from the first attempt of PICC insertion within 48 of randomisation hours until the clinical follow up for primary outcome (see table 1 in section 8.2) should be reported (see section 10.1).

These will be reported as they arise as described in section 10. An independent Data and Safety Monitoring Committee (IDSMC) will be convened to monitor safety data (see section 16.3 for further details).

**Note:** Although this is an unblinded trial all sites are expected to adhere to good practice in terms of treating babies similarly, regardless of the allocated PICC.

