## **9.6 Analysis Plan**

The trial will be analysed using the International Conference on Harmonisation E9 guidelines and reported using the 'Consolidation Standard of Reporting Trials' (CONSORT) guidelines. A full and detailed statistical analysis plan will be developed prior to the final analysis of the trial. The main features of the statistical analysis plan are included here.

The analysis of primary and secondary outcomes will use the principle of intention to treat, based on all the randomised participants, as far as is practically possible. Per protocol sensitivity analyses will also be carried out on a number of outcomes, these will be specified in the statistical analysis plan. A p-value of 0.05 or less will be used to declare statistical significance for all analyses and results will be presented with 95% confidence intervals. Baseline characteristics will be presented but no comparisons will be undertaken, rather the clinical importance of any imbalance will be noted.

Kaplan-Meier survival curves and log rank tests will be used for time to event outcomes including the primary outcome 'time to first BSI'. Continuous data will be presented as means and standard deviations and analysed using two-sample tests (if data is skewed, medians and ranges will be presented and analysis will be by Mann Whitney U tests). Binary data will be reported in terms of relative risk and analysed using chi-squared or Fisher's exact tests as appropriate.

All related adverse events (AEs) and related serious adverse events (SAEs) reported by the clinical investigator will be presented, identified by treatment group, but no formal comparisons will be made across the treatment groups.

Missing data will be monitored and strategies developed to minimise its occurrence, however as much data as possible will be collected about the reasons for missing data and this will be used to inform the handling of missing data.

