**Table 4: Reporting of Adverse Events**

	Relatedness	Expectedness	Seriousness	Reporting to MC CTU required within	Forms to complete
	For definition see section 10.2.4	For definition see section 10.2.6	For definition see section 10.2.2		
Event	Related	Not-expected	Serious 	24 hours	Form 9a: Serious Unexpected Related Adverse Events Form 9b: Medical Device Adverse Incident Report 
	Related	Expected	Serious 	7 days	Form 8: Related Adverse events
	Related	Not-expected	Not Serious	7 days	Form 8: Related Adverse events Form 9b: Medical Device Adverse Incident Report 
	Related	Expected	Not Serious	7 days	Form 8: Related Adverse events
	Not related	N/A	N/A 	None	None

 If outcome of event is death, this should also be recorded on Form 7a: Clinical Outcomes, independent of relatedness or expectedness.

 Once Form 9b: Medical Device Adverse Incident Reports is submitted to the MC CTU, it is the responsibility of the MC CTU to report the event to the Medicines and Healthcare products Regulatory Agency Adverse Incident Centre (MHRA AIC) via the online reporting system.

Flowchart Section 10.3 can also be used to determine the reporting requirements of adverse events).

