**Table 5: Definitions of Relatedness**

Relationship	Description
Unrelated	There is no evidence of any causal relationship. N.B. An alternative cause for the AE should be given.
Unlikely	There is little evidence to suggest there is a causal relationship (e.g. the event did not occur within a reasonable time after insertion of the PICC). There is another reasonable explanation for the event (e.g. the participant's clinical condition, other concomitant treatment).
Possibly*	There is some evidence to suggest a causal relationship (e.g. because the event occurs within a reasonable time after insertion of the PICC). However, the influence of other factors may have contributed to the event (e.g. the participant's clinical condition, other concomitant treatments).
Probably*	There is evidence to suggest a causal relationship and the influence of other factors is unlikely.
Almost certainly*	There is clear evidence to suggest a causal relationship and other possible contributing factors can be ruled out.

\*Those which are highlighted in green are referred to throughout the protocol as '**related**' and need to be reported as part of the trial (refer to table 4 for reporting requirements).

It is the responsibility of the investigator responsible for the care of the participant to assess each AE and assign the causality/relatedness using the definitions in Table 5.

If any doubt about the causality/relatedness exists the local investigator should inform the trial coordination centre who will notify the Chief Investigators. In the case of discrepant views on causality between the investigator and others, HRA and the MHRA AIC will be informed of both points of view.

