**Table 7: Expected AEs Associated with PICC Insertion that DO need to be recorded on Form 8: Related Adverse Events**

Adverse Event Description
Cardiac tamponade
Catheter damage
Difficulty in successfully flushing catheter or other evidence of catheter blockage
Difficulty in removing catheter
Difficulty in removing stylet
Extravasation
Hypersensitive reaction to PICC (rifampicin or miconazole)
Perforation in line
Skin damage associated with line dressing
Swelling at line site / haematoma at line site

If an event is considered **related** and is **included** in table 7 it should be reported as an **expected** AE/SAE (as applicable).

If an event is considered **related** and is **not included** in the table 7 it should be reported as an **unexpected** AE/SAE (as applicable).

[figure not shown]
Table 8 provides a list of the AEs which are **expected** as part of the trial and could be **related** to the insertion of the PICC but do not need to be recorded on Form 8: Related Adverse Events as they are captured elsewhere.

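### The device and drug-reaction events in Table 7 are recorded only if an unblinded investigator calls them related, and section 9.6 then bars comparing them, so they get no unfiltered between-arm estimate

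*Protocol*

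**What the plan says.** Section 2.2 of the protocol gives the reason for the trial: "Clear evidence is needed of the effects of AM-PICC on BSI, the safety of AM-PICC, and on cost-effectiveness", before neonatologists will change what they buy.

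The AM-PICC is visibly stained by rifampicin. The Protocol Summary concludes: "Hence, this is an unblinded trial".

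Section 8.4 makes an adverse event reportable when it is "judged by the investigator to be possibly, probably, or almost certainly related to the intervention". The text under Table 5 says who decides: "It is the responsibility of the investigator responsible for the care of the participant to assess each AE and assign the causality/relatedness". Table 4 asks for no form when an event is not related. Section 10.2.6 applies the same condition to the ten events of Table 7, which go on Form 8 when considered related.

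Section 9.6 says that related adverse events and related serious adverse events "will be presented, identified by treatment group, but no formal comparisons will be made across the treatment groups".

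Other harm-relevant information takes a different route:
- Section 4.2 lists as secondary endpoints death, NEC, chronic lung disease, treatment for retinopathy, cranial ultrasound abnormality and resistance, for example "Rifampicin resistance in any isolate from blood/CSF culture". None depends on a relatedness judgement, and section 9.6 compares secondary outcomes by intention to treat with relative risks or log-rank tests and 95% confidence intervals.
- A footnote to Table 4 covers fatal events: "If outcome of event is death, this should also be recorded on Form 7a: Clinical Outcomes, independent of relatedness or expectedness".
- The Table 8 events (resistance, suspected or confirmed BSI, thrombophlebitis, thrombosis) "do not need to be recorded on Form 8: Related Adverse Events as they are captured elsewhere", namely on Forms 5 and 6.

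**The concern.** Section 2.4.1 confines the added risk of the AM-PICC to its coating and names two forms of it: adverse drug reactions and resistant organisms. Resistance is a compared endpoint. Adverse drug reactions have no such route. They enter the data only through Form 8, after a causality judgement by someone who can see which line was used, and are then listed without comparison. The same holds for the other Table 7 events.

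Two things are at stake. First, a clinician who knows that a line carries drugs may attribute the same skin change or swelling to it more readily, or less readily, than with a plain line, so the counts by arm may differ for reasons other than the device. An event judged unrelated and not fatal leaves no record on Form 8, and no later analysis plan can recover it. Second, even for what is recorded, the plan provides no difference and no interval, on a question that section 2.2 says must be answered.

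**Working it through.** No figure in the protocol bears directly on this point, so the check is mainly a comparison of sections, followed by two illustrations with assumed rates.

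1. **Which events pass through the filter.** Table 7 has ten items.
   - Five leave room for judgement: tamponade, extravasation, hypersensitivity, skin damage at the dressing, and swelling or haematoma at the site.
   - Five are plainly mechanical: catheter damage, flushing difficulty or blockage, difficulty removing the catheter, difficulty removing the stylet, and perforation in the line. These would probably be called related in either arm.
   - The hypersensitivity item names rifampicin and miconazole, which only the AM-PICC carries. As worded, it invites recording in one arm only and gives no control rate.

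2. **What the filter can do.** Let both arms have the same true rate p, and let a₁ and a₀ be the proportions of events judged related in the AM-PICC and S-PICC arms. The recorded rates are p·a₁ and p·a₀, so their ratio is a₁/a₀ whatever p is. The protocol gives no values for a₁ or a₀. The pairs below are assumptions:
   - 50% and 50%: ratio 1.0
   - 80% and 60%: ratio 1.33 (with p = 5%, recorded rates of 4.0% and 3.0%)
   - 70% and 50%: ratio 1.4
   - 70% and 30%: ratio 2.3

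   If attribution is readier in the S-PICC arm, the ratio falls below 1. If nearly every event is called related in both arms, as is likely for mechanical faults, it stays near 1.

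3. **What an interval could show.** Section 9.4 plans 429 babies per arm (408/0.95 = 429.5, which agrees with the stated figure apart from rounding). At a common rate p, the 95% half-width for a risk difference is 1.96 × √(2p(1−p)/429). Event rates are assumed:
   - p = 1%: 1.96 × √(0.0198/429) = 1.3 points
   - p = 2%: 1.96 × √(0.0392/429) = 1.9 points
   - p = 5%: 1.96 × √(0.0950/429) = 2.9 points
   - p = 10%: 1.96 × √(0.1800/429) = 4.0 points

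   With 408 per arm in place of 429, to allow for babies without an insertion attempt or follow-up, these become 1.4, 1.9, 3.0 and 4.1.

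4. **Limits at low rates.** At 1% about 4 events per arm are expected (429 × 0.01 = 4.3), so the normal approximation is rough and an exact or score interval is needed. With no events in 429 babies, the one-sided 95% upper bound is 1 − 0.05^(1/429) = 0.7%. For rare events the interval is wide relative to the rate, but it still bounds the excess risk.

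**The case against.** A reader might infer that harms of every kind are recorded only when judged related, that section 9.6 forbids any comparison of harms, and that the trial therefore cannot say how safe the coated line is. The protocol does not support this. The endpoints in section 4.2 include death, four serious neonatal morbidities and rifampicin resistance. All are collected without a causality test and formally compared. Resistance is one of the two risks that section 2.4.1 names, and it forms the first two secondary objectives. Thrombosis and thrombophlebitis go on Form 6, although neither is a listed endpoint.

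The attribution argument can also be pressed too far. Section 10.2.4 judges relatedness against PICC insertion, which both arms share, and a possible relation is enough. Eight of the ten Table 7 items are worded by reference to the line or its site, so an unrelated version of most of them hardly exists. This stands, and it is why the concern is small for mechanical events. It does not dispose of tamponade and extravasation, nor of deciding whether skin damage or swelling is due to the line or its dressing. For hypersensitivity it shows that the item itself needs rewording.

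Related-only reporting is also a defensible economy for CE-marked devices used as intended, with an IDSMC and monitoring of reporting rates across sites. But for these events the IDSMC sees the same filtered data. Nor does the request in section 8.4 that sites treat babies alike deal with attribution.

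Finally, listing adverse events by arm without tests is common, and interval estimates are often left to the analysis plan. That makes the analysis half of the point the weaker one. It remains because section 9.6 itself excludes the comparison. The capture rule is the stronger half.

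**Conclusion.** The point holds for the Table 7 events and no further. Recording them depends on a causality judgement made with knowledge of allocation, and section 9.6 then excludes a formal comparison, so the trial yields no unfiltered between-arm estimate for them. It is a worthwhile, inexpensive improvement and does not threaten the trial's main conclusions.

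The size of any bias is unknown. Spurious ratios from 1.0 to 2.3 follow only from the attribution rates assumed above, and nothing in the protocol says that differential attribution will occur. What would be gained is better defined: risk-difference intervals of about ±1.3 to ±2.9 points at assumed event rates of 1% to 5%, taking all 429 babies per arm as the denominator.

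**What to change.** In sections 8.4, 10.1 and 10.2.6, with Table 4 to match, require the ten Table 7 events to be recorded on Form 8 in both arms over the existing reporting window, with relatedness kept as a separate field and no longer the condition for recording. Reword the hypersensitivity item as clinical signs, so that it can be recorded with either line. Reporting timelines for related events need not change.

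In section 9.6, replace the no-comparison rule for these events with the following: for each event and for any event, the number of babies affected per arm and the risk difference with its 95% confidence interval, exact or score-type where events are sparse, without p-values, among babies with an insertion attempt.

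The cost is a few more Form 8 entries and one extra table. Daily follow-up forms are already completed for every baby (section 6.5), so no new visits or procedures are needed. Intervals for rare events will be wide and should be presented as such.

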## 10 SAFETY REPORTING

### 10.1 Reporting of Adverse Events

The table below (table 4) provides an overview of the reporting requirements for any adverse events occurring between the first attempt of PICC insertion following randomisation until the clinical follow up for primary outcome (see table 1 section 8.2).

The definitions detailed later in section 10 should be utilised to confirm that correct reporting is achieved.

**Table 4: Reporting of Adverse Events**

	Relatedness	Expectedness	Seriousness	Reporting to MC CTU required within	Forms to complete
	For definition see section 10.2.4	For definition see section 10.2.6	For definition see section 10.2.2		
Event	Related	Not-expected	Serious 	24 hours	Form 9a: Serious Unexpected Related Adverse Events Form 9b: Medical Device Adverse Incident Report 
	Related	Expected	Serious 	7 days	Form 8: Related Adverse events
	Related	Not-expected	Not Serious	7 days	Form 8: Related Adverse events Form 9b: Medical Device Adverse Incident Report 
	Related	Expected	Not Serious	7 days	Form 8: Related Adverse events
	Not related	N/A	N/A 	None	None

 If outcome of event is death, this should also be recorded on Form 7a: Clinical Outcomes, independent of relatedness or expectedness.

 Once Form 9b: Medical Device Adverse Incident Reports is submitted to the MC CTU, it is the responsibility of the MC CTU to report the event to the Medicines and Healthcare products Regulatory Agency Adverse Incident Centre (MHRA AIC) via the online reporting system.

Flowchart Section 10.3 can also be used to determine the reporting requirements of adverse events).

## 10.2 Terms and Definitions

### 10.2.1 Adverse Event (AE)

An **Adverse Event (AE)** is defined as any untoward medical occurrence in a participant to whom a research procedure has been administered, including occurrences which are not necessarily caused by or related to that procedure.

### 10.2.2 Serious Adverse Event (SAE)

**Serious Adverse Event (SAE)** is an untoward occurrence that:

- Results in death;
- Is life-threatening\*;
- Requires in-patient hospitalisation or prolongation of existing hospitalisation\*\*
- Results in persistent or significant disability or incapacity, or;
- Consists of a congenital anomaly or birth defect;
- Other important medical events\*\*\*.

\*'life-threatening' in the definition of 'serious' refers to an event in which the patient was at risk of death at the time of the event; it does not refer to an event which hypothetically might have caused death if it were more severe.

\*\*Hospitalisation is defined as an inpatient admission, regardless of length of stay, even if the hospitalisation is a precautionary measure for continued observation. Hospitalisations for a pre-existing condition, including elective procedures that have not worsened, do not constitute an SAE.

\*\*\*Other important medical events that may not result in death, be life-threatening, or require hospitalisation may be considered a serious adverse event/experience when, based upon appropriate medical judgment, they may jeopardise the subject and may require medical or surgical intervention to prevent one of the outcomes listed in this definition.

**Note:** It is the responsibility of the PI or designated to grade an event as 'not serious' (AE) or 'serious' (SAE).

